4.3 Stopping Criteria

All AEs should be considered possibly related to study drug unless clearly unrelated or if there is a clear etiology other than study drug such as a pre-existing medical condition, an underlying disease, or a concomitant medication. The decision to have an associated pause in enrollment will be made by the chairperson of the iDMC (with input from the Medical Monitor). The iDMC will oversee the safety and tolerability of FP-025 during the study and determine if it is acceptable to continue, as described in Section 9.2.4. However, safety and tolerability data will be reviewed on an ongoing basis by the Medical Monitor and stopping rules will be applicable starting with dosing of the first patient.

4.3.1 Criteria for Potential Interruption or Discontinuation of Study Drug in Individual Patients

In the event that any of the following is encountered, the Investigator, Sponsor, or Medical Monitor may choose to interrupt the study drug (in consultation with the Medical Monitor) or discontinue a patient from the study drug (but continue to follow the patient for safety and key efficacy endpoints):

- \geq Grade 3 (Common Terminology Criteria for Adverse Events [CTCAE] version 5.0) AE or clinically significant laboratory abnormality considered related to study drug;

Note: All \geq Grade 3 (CTCAE) laboratory abnormalities should be confirmed with a repeat test within 24 hours to confirm the abnormality.

- Severe anaphylactic reaction, including bronchospasm; or
- Requirement for a prohibited concomitant medication (eg, non-standard of care concomitant medications for COVID-19).

For any patient who prematurely discontinues from study drug, the reason and date of discontinuation will be documented in the electronic case report form (eCRF) and the patient should continue to complete all safety assessments at subsequent study visits.

4.3.2 Criteria for Potential Study Termination

In the event that any of the following is encountered, the iDMC will convene to determine if the study must stop enrollment and/or to recommend modification to the protocol (ie, decrease or change the dose of study drug, modify dosing schedule, or terminate the study, as described in the iDMC Charter):

- \geq Grade 4 (CTCAE version 5.0) reaction considered related to study drug;
- \geq 3 patients are discontinued from treatment for safety reasons; or
- \geq 3 patients experience similar SAEs or Grade 3 (CTCAE version 5.0) AEs regardless of relatedness to study drug.

Note: All \geq Grade 3 (CTCAE) laboratory abnormalities should be confirmed with a repeat test within 24 hours to confirm the abnormality.

The following will not be considered as criteria for study termination:

- Grade 3 nausea if resolves to \leq Grade 1 within 72 hours;
- Grade 3 fatigue, malaise, or insomnia if resolves to \leq Grade 1 within 72 hours; and
- \leq Grade 4 isolated electrolyte abnormalities that resolve with or without intervention to \leq Grade 1 within 72 hours.

4.4 Withdrawal Criteria

Participation of a patient in this study may be discontinued for any of the following reasons:

- Withdrawal of consent or request for discontinuation from the study for any reason; and
- Loss to follow-up.

If a patient withdraws prematurely from the study due to the above criteria or any other reason, study staff should make every effort to complete the full panel of assessments scheduled for the Early Termination Visit. The reason for patient withdrawal must be documented in the eCRF.

In the case of patients lost to follow-up, attempts to contact the patient must be made and documented in the patient's medical records.

Study drug treatment may be discontinued (although the patient should be encouraged to remain in the study and to follow-up for key study visits) for any of the following reasons:

- Occurrence of any medical condition or circumstance that exposes the patient to substantial risk and/or does not allow the patient to adhere to the requirements of the protocol;
- Any SAE, clinically significant AE, severe laboratory abnormality, intercurrent illness, or other medical condition which indicates to the Investigator that continued participation is not in the best interest of the patient;

Note: Patients who discontinue study drug for safety or tolerability reasons will not be replaced.

- Pregnancy; or
- Patient failure to comply with protocol requirements or study-related procedures.

5 STUDY TREATMENTS

5.1 Treatment Groups

During Phase 2, patients will be randomized in a 1:1:1 ratio to receive FP-025 100 mg BID, FP-025 300 mg BID, or placebo BID for 28 days, starting on Day 1 (Visit 2). Patients in each dose group will receive a total of 6 capsules during each dosing session as follows:

- FP-025 100 mg BID: Two 50 mg capsules and 4 placebo capsules;
- FP-025 300 mg BID: Six 50 mg capsules; and
- Placebo: 6 placebo capsules.

Based on the results of the primary analysis of Phase 2, 1 optimal dose will be selected to carry into Phase 3, and patients will be randomized in a 1:1 ratio to receive FP-025 or placebo for 28 days. No dose adjustments will be performed for renal impairment.

5.2 Rationale for Dosing

Preclinical and clinical studies suggest that administration of FP-025 in doses of 100 mg to 300 mg BID for 28 days in COVID-19 patients should be safe and efficacious. In healthy subjects, FP-025 has been found to be safe and well tolerated at dosages up to 400 mg BID for 7 days. Efficacy has been demonstrated in non-clinical studies, including the LPS-induced acute lung injury study in mice, at doses of 10 mg/kg and below, which is lower than the human equivalents of 100 mg and 300 mg. At those levels, the projected plasma exposure of FP-025 would be lower than the doses of 100 and 300 mg. A clinical study in patients with asthma is ongoing and remains blinded. The dose level of FP-025 in that study is 400 mg BID for 12 days.

5.3 Randomization and Blinding

During Phase 2, patients will be randomized in a 1:1:1 ratio to receive FP-025 100 mg BID, FP-025 300 mg BID, or placebo BID for 28 days. Patients in each dose group will receive a total of 6 capsules during each dosing session as described in Section 5.1 in order to maintain blinding. Randomized patients will be stratified by the use of invasive mechanical ventilation at the time of randomization (yes or no). Patients, Investigators, and study personnel involved in the administration and assessment of the study drug will be blinded to the patient treatment assignments throughout the study.

5.4 Breaking the Blind

Unblinding by request of an Investigator should occur only in the event of an emergency or AE for which it is necessary to know the study drug to determine an appropriate course of therapy for the patient. If the Investigator must identify the treatment assignment of an individual patient, the Investigator or qualified designee should request the treatment assignment from the centralized randomization system. The Investigator is advised not to reveal the study drug assignment to other centers or Sponsor personnel.

Prior to unblinding, and if the situation allows, the Investigator should consult with the Medical Monitor. If this is impractical, the Investigator must notify the Medical Monitor as soon as possible, without revealing the treatment assignment of the unblinded patient. The Investigator must

document the patient identification and the date and time for breaking the blind and must clearly explain the reasons for breaking the blind.

Medically necessary care should not be delayed for unblinding information (ie, the Investigator should treat the patient based on the patient's signs/symptoms without waiting for the unblinding process to be completed).

Patients who are unblinded and discontinue study drug but are not withdrawn from the study should continue to complete all safety assessments at subsequent study visits.

5.5 Drug Supplies

5.5.1 Formulation and Packaging

FP-025 is supplied as an oral capsule (amorphous solid dispersion-in-capsule) at a dose strength of 50 mg per capsule.

Foresee will supply sufficient quantities of study drug (FP-025 and matching placebo) to allow for completion of the study. The lot numbers will be recorded in the final clinical study report.

5.5.2 Study Drug Preparation and Dispensing

The study drug (FP-025 and matching placebo) will be dispensed by the pharmacist or qualified designee.

5.5.3 Study Drug Administration

The study drug (FP-025 and matching placebo) will be administered orally as capsules or via a polyvinyl chloride nasogastric tube (by opening up the capsules and delivering as a suspension in orange juice). Capsules can also be opened and added to orange juice to drink. During Phase 2, each patient will receive either FP-025 (100 mg or 300 mg) or placebo BID for 28 days. Based on the results of the primary analysis of Phase 2, 1 optimal dose will be selected to carry into Phase 3, and patients will be randomized in a 1:1 ratio to receive FP-025 or placebo for 28 days.

5.5.4 Treatment Compliance

To ensure treatment compliance, all inpatient doses will be administered by center staff.

For outpatients, treatment compliance will be assessed by pill counts. Center staff will counsel patients on the importance of adhering to the study drug administration schedule prior to hospital discharge. At the next inpatient visit on Day 28, center staff will count the number of capsules left in the bottle and compare that to the number of capsules the patient was given at hospital discharge.

The exact time of study drug administration and the volume of study drug administered will be recorded in the eCRF.

5.5.5 Storage and Accountability

At the center, FP-025 will be stored at room temperature (ie, 20°C to 25°C [68°F to 77°F]) under secure conditions.

The pharmacist (or designee) will acknowledge receipt of all shipments of the study drug and maintain an inventory. The study drugs must be kept in a locked area with restricted access and

stored and handled in accordance with the manufacturer's instructions. The pharmacist (or designee) will also keep accurate records of the quantities of the study drugs dispensed and used by each patient. The clinical research associate (CRA) will periodically check the supplies of study drugs held by the pharmacist to verify accountability of all study drugs used.

At the conclusion of the study, the CRA will account for all used and unused study drug. After completion of the study, or if it is prematurely terminated, all unused materials will be returned to the Sponsor or a delegate. Additional information can be found in the Pharmacy Manual.

5.6 Prior and Concomitant Medications and/or Procedures

5.6.1 Excluded Medications and/or Procedures

The following medications, taken within 4 weeks or 5 half-lives, whichever is longer, are prohibited:

- Systemic immunomodulatory therapy that is not considered standard of care treatment for COVID-19 (eg, calcineurin inhibitors, hydroxychloroquine, anti-cytokine therapies, or Janus kinase inhibitors);

Note: Corticosteroids, including dexamethasone, in doses used for standard of care treatment for COVID-19 are allowed.

Note: Corticosteroids that are being used for other indications are also allowed as long as the daily prednisone (or other corticosteroid equivalent) dose is ≤ 10 mg. Inhaled corticosteroids and nasal corticosteroids are also acceptable.

Note: As therapies for COVID-19 are rapidly evolving, other medications that may be considered standard of care can be considered with prior approval from the Sponsor or Medical Monitor.

- Strong cytochrome P450 inducers or inhibitors as listed in Appendix E; or
- Any other investigational therapeutic products.

5.6.2 Documentation of Prior and Concomitant Medication Use

Any investigational and off-label therapies for COVID-19-related infections for each patient (eg, hydroxychloroquine or interleukin [IL]-6 inhibitors), along with the time, dose, and duration of their administration, must be recorded. All patients will be allowed to receive standard of care and/or EUA medications and treatment for COVID-19; however, the study drug should be discontinued for other non-standard of care concomitant medications used with the intent of directly treating COVID-19 unless there is prior Medical Monitor or Sponsor approval for the patient to remain on the study drug. If the use of concomitant medications necessitates study drug discontinuation, the patient should be encouraged to remain in the study and to follow-up for key study visits (Day 28 and Day 60) but will not be required to attend every study visit. If the patient withdraws, he/she should complete the Early Termination Visit.

Any treatment given in addition to the study drug during the study is regarded as a concomitant medication and must be recorded on the appropriate eCRF.

Any relevant medications received in the 14 days prior to study drug administration must be recorded on the appropriate eCRF, along with the reason for use, dates of administration, and dosages.

Concomitant medications should be kept to a minimum during the study. However, if these are considered necessary for the patient's welfare and are unlikely to interfere with the study drug, they may be given at the discretion of the Investigator and recorded in the patient's source documents and the eCRF.

Any care decisions that are made due to resource limitation (eg, ventilation not available) must be documented.

Data surrounding major changes in background therapy will be collected. The standard of care that is followed for each patient and center must be recorded. If standard of care therapies are not able to be delivered due to resource limitations, this should also be recorded.

Any reasons for discontinuation of ventilation must be recorded on the appropriate eCRF, including all data related to clinical decision making that guides removal from mechanical ventilation in relation to clinical deterioration or lack of clinical response.

6 STUDY PROCEDURES

Study procedures will follow the Schedule of Procedures in Appendix A.

7 EFFICACY AND PHARMACOKINETIC ASSESSMENTS

7.1 Efficacy and Pharmacokinetic Endpoints

For all endpoints defined by events, the time points are defined as the number of days after randomization.

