Standard of care procedures for mechanical ventilation (eg, low tidal volume protective mechanical ventilation) and standard of care procedures for weaning from mechanical ventilation will be followed. The clinical criteria for weaning readiness testing and discontinuation from mechanical ventilation are described in Appendix D.

Study drug administration will begin on Day 1 (Visit 2) following randomization. All patients will receive standard of care and/or EUA treatment for COVID-19 in addition to the study drug. Patients will continue study drug treatment BID through Day 27 and take 1 dose on Day 28. If a patient is discharged from the hospital prior to Day 28, he/she will continue treatment as an outpatient at home with his/her assigned treatment (FP-025 100 mg BID, FP-025 300 mg BID, or placebo BID) until Day 28. Dosing instructions will be provided prior to discharge. Although treatment will be identical for inpatients and outpatients, patients discharged from the hospital will follow a different Schedule of Procedures, characterized by telemedicine (or telephone, if sites and/or patients do not have video capability) visits. The End of Treatment (EOT) Visit on Day 28

will be identical for all patients (with the exception of the arterial oxygen partial pressure [PaO₂]/fractional inspired oxygen [FiO₂] ratio, performed only in patients on invasive or non-invasive ventilation) and will include a high-resolution, non-contrast CT scan, in addition to other assessments.

After treatment is completed, all patients will undergo 2 follow-up assessments during the Follow-Up Period. The first follow-up will be a telephone visit on Day 45 to assess concomitant medications, adverse events (AEs), and the NIAID 8-point ordinal scale for COVID-19 and hospitalization outcomes score. The second follow-up will be an in-person visit on Day 60 and will include a high-resolution, non-contrast CT scan and pulmonary function tests, in addition to other assessments.

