7.1.2 Key Secondary Efficacy Endpoints

The key secondary efficacy endpoints include the following, with each dose (Phase 2) or the optimal dose (Phase 3) of FP-025 compared to placebo:

- Proportion of patients on invasive mechanical ventilation at Day 28;
- Proportion of patients alive at Day 28;
- Proportion of patients alive and not requiring non-invasive or invasive ventilation (ie, not receiving high-flow nasal cannula, non-invasive positive pressure ventilation, invasive mechanical ventilation, or ECMO) at Day 60;
- Proportion of patients on invasive mechanical ventilation at Day 60; and
- Proportion of patients alive at Day 60.

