APPENDIX A: SCHEDULE OF PROCEDURES

Table 2. Schedule of Procedures: Inpatient Admission Through Day 28

	Screening Visit	Treatment Period							Follow-Up Period		ET Visit ^b
		1	2	3	4	5	6	7/EOT	8	9	
Visit	-1 to 1	1	4	7	14	21	28	45 ^a	60		
Study Day											
Visit Window (Days)	-	±3	±3	±3	±3	±3	±3	±3	±7	±7	Unscheduled
Informed consent ^c	X										
I/E criteria	X	X ^d									
Demographic information	X										
Medical/surgical history	X	X ^d									
Assessment of standard of care ^e		X-----X									
Prior/concomitant medications	X	X-----X							X	X	X
Weight and height ^f	X	X						X		X	X
Physical examination ^g	X	X	X	X	X	X	X			X	X
Vital signs including SpO ₂ ^h	X	X	X	X	X	X	X			X	X
PaO ₂ /FiO ₂ ratio ⁱ	X	X	X	X	X	X	X			X	X
hCG ^j	X						X			X	X
Viral respiratory panel ^k	X										
12-lead ECG ^l		X	X	X	X	X	X				X
SARS-CoV-2 PCR ^m	X										
Clinical laboratory assessments ⁿ	X	X	X	X	X	X	X		X		X
PK blood sampling ^o		X	X	X	X	X	X				
Randomization		X									

Footnotes at the end of table.

Table 2. Schedule of Procedures: Inpatient Admission Through Day 28 (Continued)

	Screening Visit	Treatment Period							Follow-Up Period		ET Visit ^b
		1	2	3	4	5	6	7/EOT	8	9	
Visit	-1 to 1	1	4	7	14	21	28	45 ^a	60		
Study Day											
Visit Window (Days)	–	±3	±3	±3	±3	±3	±3	±7	±7	Unscheduled	
Study drug administration ^b		X	X	X	X	X	X				
High resolution, non-contrast CT scan of the chest ^a	X						X		X	X	
PFTs ^c									X	X	
Biomarker assessment (blood) ^d		X		X	X		X		X	X	
NIAID 8-point ordinal scale assessment		X	X	X	X	X	X	X	X	X	
AEs/SAEs ^e	X							X		X	

Note: If the study drug is discontinued but the patient is remaining in the study, the patient should be encouraged to remain in the study and to follow-up for key study visits (Day 28 and Day 60) but will not be required to attend every study visit. If the patient withdraws, he/she should complete the ET Visit.

- a. The Day 45 visit will be a telephone visit only.
- b. If a patient withdraws prematurely from the study, study staff should make every effort to complete the full panel of assessments scheduled for the ET visit. The reason for patient withdrawal must be documented in the eCRF.
- c. The Investigator will obtain written informed consent from each patient before any study-specific activity is performed.
- d. I/E criteria and medical/surgical history will be reviewed again on Day 1 (Visit 2) prior to randomization. Any updates since the Screening Visit will be assessed.

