AE = adverse event; BAL = bronchoalveolar lavage; BID = twice daily; C4M = neo-epitope of MMP-2, 9-, and 12-mediated degradation of type IV collagen; C6M = neo-epitope of MMP-2-mediated degradation of type VI collagen; CoV = coronavirus; CRPM = neo-epitope of MMP-1 and 8-mediated degradation of C-reactive protein; CT = computed tomography; ECG = electrocardiogram; eCRF = electronic case report form; EOT = End of Treatment; ET = Early Termination; FEV₁ = forced expiratory volume in 1 second; FiO₂ = fractional inspired oxygen; FVC = forced vital capacity; hCG = human chorionic gonadotropin; I/E = inclusion and exclusion; ICF = informed consent form; IFN = interferon; IL = interleukin; MMP = matrix metalloproteinase; NIAID = National Institute of Allergy and Infectious Diseases; PaO₂ = arterial oxygen partial pressure; PCR = polymerase chain reaction; PFT = pulmonary function test; PK = pharmacokinetic(s); PRO-C3 = released N-terminal pro-peptide of type III collagen; PRO-C4 = internal epitope in the 7S domain of type IV collagen; PRO-C6 = C-terminal of released C5 domain of type VI collagen α 3 chain (endotrophin); reC1M = neo-epitope of MMP-2, 9-, and 13-mediated degradation of type I collagen; SARS = severe acute respiratory syndrome; SpO₂ = peripheral capillary oxygen saturation; TGF = transforming growth factor; TNF = tumor necrosis factor; WCBP = woman/women of childbearing potential; X-FIB (D-dimer) = neo-epitope of plasmin-mediated degradation of cross-linked fibrin.

Table 3. Modified Schedule of Procedures for Discharged Patients

Visit	Treatment Period					Follow-Up Period		ET Visit ^f
	Day of Discharge ^a	O1 ^b	O2 ^b	O3 ^b	11/EOT	12	13	
Study Day	X ^c	X + 7 ^d	X + 14 ^d	X + 21 ^d	28	45 ^e	60	
Visit Window (Days)	±2	±3	±3	±3	±3	±7	±7	Unscheduled
Assessment of standard of care treatment ^g	X-----				X			
Prior/concomitant medications	X-----				X	X	X	
Weight	X				X		X	X
Physical examination ^h	X	X	X	X	X		X	X
Vital signs including SpO ₂ ⁱ	X	X	X	X	X		X	X
Urine hCG ^j					X		X	X
12-lead ECG ^k	X				X			X
Clinical laboratory assessments ^l	X				X		X	X
PK blood sampling ^m					X			
Study drug provided for rest of study period	X							
Study drug self-administration ⁿ		X	X	X	X			
High resolution, non-contrast CT scan of the chest					X		X	X
PFTs ^o							X	X
Biomarker assessment (blood) ^p	X				X		X	X
NIAID 8-point ordinal scale assessment	X				X	X	X	X
AEs/SAEs ^q	X	X-----					X	X

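### The last scheduled contact may fall on study Day 53, so discharged patients seen early have no planned observation of ventilation status at Day 60

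*Combined protocol and SAP*

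**What the plan says.** Section 7.1 fixes the clock: "For all endpoints defined by events, the time points are defined as the number of days after randomization". Section 7.1.2 lists the key secondary endpoints. In the Phase 3 testing order of Section 9.2.1.3, the third is being alive without ventilatory support at Day 60, the fourth is invasive mechanical ventilation at Day 60, and the fifth is "Proportion of patients alive at Day 60".

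Section 3.1.1 describes follow-up: "After treatment is completed, all patients will undergo 2 follow-up assessments during the Follow-Up Period". The first is a telephone call on Day 45 that includes the NIAID ordinal score. For the other, "The second follow-up will be an in-person visit on Day 60". In Appendix A, Tables 2 and 3, the windows are ±3 days for Day 28 and ±7 days for both Day 45 and Day 60. No contact is scheduled after the Day 60 visit.

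Randomization falls on study Day 1. Section 3.1.1 states "Study drug administration will begin on Day 1 (Visit 2) following randomization", and a footnote to Table 2 states "I/E criteria and medical/surgical history will be reviewed again on Day 1 (Visit 2) prior to randomization".

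Adverse events and serious adverse events are collected to Day 60 (Sections 8.1 and 8.3). Section 8.1.4 keeps progression of COVID-19 out of adverse event reporting unless it is related to study drug or a study procedure, or is fatal. Section 9.2.1 counts as failures those who die, or stop treatment for lack of efficacy, and whose status cannot be determined. It leaves other data handling to the SAP.

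**The concern.** The Day 60 endpoints are status at a fixed time, but the visit that records the status may come up to a week before that time, and nothing follows it. A patient who has gone home, attends on Day 53, and is readmitted and ventilated on Day 57 would be recorded as free of support unless someone looks again. The schedule does not ask anyone to look.

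Three steps of the alpha-controlled Phase 3 hierarchy rest on Day 60 status. Status that was not collected at the time may not be recoverable later, and a SAP can only choose how to handle the gap.

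**Working it through.** **1. The plan's own figure.** Section 9.2.5 gives 304 patients for 60% versus 75%, one-sided 0.025, about 80% power. With pooled variance, the number per arm is [1.96·√(2·0.675·0.325) + 0.842·√(0.60·0.40 + 0.75·0.25)]² / 0.15² ≈ 152, so 304 in total. The figure reproduces, and this point does not change it.

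**2. Where the contacts can fall.** Randomization is on Day 1, so days after randomization = study day − 1.

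| Contact | Study days allowed | Days after randomization |
|---|---|---|
| Day 28 ±3 | 25 to 31 | 24 to 30 |
| Day 45 ±7 | 38 to 52 | 37 to 51 |
| Day 60 ±7 | 53 to 67 | 52 to 66 |

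The earliest Day 60 visit is 60 − 53 = 7 days short by study day, or 60 − 52 = 8 days short on the clock of Section 7.1. A visit exactly on study Day 60 is 60 − 59 = 1 day short on that clock. The Day 45 call always precedes the Day 60 endpoint time and always follows the Day 28 endpoint time.

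**3. What covers the gap before Day 60.**
- Patients still in hospital: the chart.
- Deaths: reportable as serious adverse events to Day 60, and Section 8.2 requires fatal progression to be recorded as one. No scheduled contact would find them.
- Non-fatal return to ventilatory support from COVID-19 progression after discharge: generally not reportable under Section 8.1.4, and no contact is scheduled.

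Endpoints three and four therefore lack a planned observation for discharged patients seen early. Endpoint five has a reporting route but no scheduled contact to feed it.

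**4. Size at Day 60.** The documents give neither the spread of visit dates nor the rate of change near Day 60. Assume visits spread evenly over the 15 days 53 to 67, and that 1% to 3% of patients change status per week.
- Share seen before Day 60: 7/15 = 47%.
- Mean shortfall among them: (7+6+5+4+3+2+1)/7 = 4 days.
- Mean shortfall over all patients: 28/15 = 1.87 days = 0.267 week.
- Misclassified: 0.267 × 1% = 0.27% to 0.267 × 3% = 0.80%.
- Of 304: 0.8 to 2.4 patients, so roughly 1 to 2.

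On the literal clock (endpoint on study Day 61), the mean shortfall is (8+7+…+1)/15 = 36/15 = 2.4 days = 0.343 week, giving 0.34% to 1.03%, or 1.0 to 3.1 of 304. The conclusion is the same. Both results assume that nothing is recovered from charts or safety reports, so at these rates they err on the high side.

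**5. Day 28.** Over Days 25 to 31, the mean early shortfall is (3+2+1)/7 = 0.86 day. At an assumed 2% to 5% per week, that gives 0.24% to 0.61% if no later contact existed. Two later contacts do exist, so the effect at the final analysis should be smaller.

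**The case against.** The strongest reply is that the plan needs dated records, not only visit snapshots. Ventilator-free, ICU-free and hospital days to Day 60 (Section 7.1.3) cannot be computed without dates, Section 5.6.2 requires reasons for stopping ventilation on the case report form, and timing endpoints from randomization suggests that the visit date was never meant to define them. Readmission for reasons other than COVID-19 progression would normally be a serious adverse event. This stands in part: it narrows the gap to a few discharged patients. It does not close it, because nothing tells sites to learn what happened between an early visit and Day 60.

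A reader might infer more than the documents support:
- **That the primary endpoint is compromised.** A patient seen on Day 25 is called around Day 45 and seen around Day 60, so Day 28 survival is recoverable and ventilation can be dated afterwards. The Phase 2 primary analysis and the Phase 3 interim are triggered by the Day 28 visit and may precede those contacts for the last patients, but this does not reach the final analysis.
- **That Day 60 status cannot be observed, or will be carried forward or set to missing.** The text says none of this. An in-window visit may simply be taken as the Day 60 assessment, and the SAP wording on data handling was not in the text reviewed.
- **That power falls materially.** If 25% had no Day 60 status, power at the planning rates would be 68% with them excluded or 50% with all counted as failures. Neither rule is in the plan, and the 60% and 75% rates are for the primary endpoint.
- **That the one-day difference in clocks biases the result.** It lies well inside the windows, applies to both arms, and is not shown to change any result.

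**Conclusion.** The point holds in a narrow form. Patients discharged and then seen on study Days 53 to 59 have no planned observation of ventilation status at Day 60, which affects key secondary endpoints three and four. For endpoint five, deaths are reportable but no contact is scheduled to find them. The size, roughly 1 to 2 of 304 patients, rests on an assumed even spread of visits and an assumed 1% to 3% weekly rate of change. Symmetric visit windows are a legitimate design choice. What is missing is a status check at the endpoint date. Minor severity: a cheap improvement rather than the repair of an error.

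**What to change.** In Appendix A, Tables 2 and 3, keep the ±7-day window for CT, pulmonary function and laboratory tests. Add that, for anyone seen before the Day 60 endpoint date, vital status and respiratory support are to be ascertained for that date by a phone call or records check made on or after it. In the same edit, state one day count for Day 28 and Day 60, either study day with randomization as Day 1 or days since randomization, and use it in Section 7.1 and Appendix A.

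The cost is one call or records check per patient seen early, plus the wording change. The sample size stays at 304.
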